9.5. Multiple Imputation for NYHA Class analysis

CMH method incorporating multiple imputation (MI) will be the primary analysis method for NYHA class. The change from baseline in NYHA class at Month 30 will be dichotomized into two categories: stable or improved vs. worsened. For missing due to death (including heart transplant and LVAD placement), missing NYHA class values will be imputed as Class IV. For missing not due to death, the missing NYHA class values will be assumed as MAR and multiply imputed using the MCMC procedure for each treatment and baseline tafamidis use group, with information including baseline NYHA class, type of amyloidosis (hATTR vs. wtATTR), age at randomization (<75 vs. \geq 75), baseline NT-proBNP, and all postbaseline NYHA class assessments at the scheduled visits as covariates. The sample code is provided below:

```
proc mi data=DATAIN out=DATA_STEP1 seed=xxx n impute=100 round=1;
  em maxiter=1000 converge=1e-10 itprint outem=outem;
  var baseline_variables base aval6m aval12m aval18m aval24m aval30m;
  by treatment bltaf;
  mcmc chain=multiple initial=em impute=full prior=ridge=0.75 niter=500
  nbiter=500;
run;
```

One hundred imputed datasets will be generated from the MI MCMC procedure using SAS PROC MI. Each of the imputed datasets will then be analyzed using the CMH method stratified by baseline NT-proBNP. The overall population analysis will also be stratified by baseline tafamidis use.

The resulting estimates (common risk difference and standard errors) from the 100 imputed datasets will be combined using SAS PROC MIANALYZE to produce inferential results (difference in proportion of being stable or improved, 95% CI, and the P value) [Rubin 1996]. Combined difference will be calculated as the average of the 100 complete-data estimates. A total variance estimate will be calculated as a weighted sum of within-imputation variance, which is the average of the complete-data variance estimates, and a between-imputation variance term. Complete details may be found in the SAS documentation for the MIANALYZE procedure (see Combining Inferences from Imputed Data Sets under Details:

<http://support.sas.com/documentation/onlinedoc/stat/131/mianalyze.pdf>).

9.6. Joint Frailty Model for the Analysis of Recurrent CV Events

Joint frailty models (JFM)[Rondeau 2007] not only address the dependency among the recurrent events, but also the dependency between recurrent events and the terminal event as well as informative censoring of recurrent events due to the terminal event. They model the recurrent events with a random-effect proportional intensity model where the subject-level random-effect v_i is called the frailty parameter, which has a gamma distribution with unit mean and variance θ . The frailty parameter accounts for the heterogeneity among patients on the intensity/rate of recurrent event (and the risk of the terminal event) that cannot be explained by the covariate vector Z_i . $\theta=0$ indicates that there is no subject-to-subject variation beyond that explained by covariate vector Z_i .

The terminal event is modeled via a random-effect proportional hazard model with the random effect being v_i^γ and γ indicates the strength of association between the terminal event and recurrent events. A positive value of γ indicates that risk of the terminal event is positively correlated with the intensity of recurrent events; a negative value of γ indicates that risk of the terminal event is negatively correlated with the intensity of recurrent events; and $\gamma=0$ indicates that risk of the terminal event is uncorrelated with the intensity of recurrent events. This method estimates the regression parameters α (for the terminal event) and β (for recurrent events) as well as θ and γ . $r_0(t)$ and $\lambda_0(t)$ are the baseline hazard functions for the recurrent events and the terminal event, respectively. A parametric model – piecewise constant functions – will be used to approximate the baseline hazard function for both recurrent events and the terminal event.

$$r_i(t) = v_i \exp(\beta^T Z_i) r_0(t)$$
$$\lambda_i(t) = v_i^\gamma \exp(\alpha^T Z_i) \lambda_0(t)$$

Simulation studies [Liu 2004; Rondeau 2007] show that when $\gamma = 0$, the JFM and reduced model (i.e., modeling recurrent events alone) give very similar regression parameter estimates and variance estimates for the recurrent events. In this case, the reduced model is acceptable. However, when $\gamma > 0$ indicating positive correlation between rate of recurrent events and death, reduced model generates biased regression parameter estimates for the recurrent events (biased towards null or underestimated effects on recurrence rate), while regression parameter estimates from JFM are practically unbiased.

Model fit criteria

Model fit for JFM will be checked via the testing of $\gamma = 0$. An insignificant result indicates little correlation between recurrent events and death which supports a reduced model.

Software implementation

The JFM model will be estimated using R package “frailtypack” version 3.5.1 ([Rondeau 2012];[Krol 2017]).

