3.4. Number of Planned Patients

The planned enrollment for this study is 600 patients.

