10.4. Amendment History

10.4.1. Amendment 5 Summary of Changes

The primary purpose for this global protocol amendment is to expand the analysis of the existing primary endpoint to both the overall population and the vutrisiran monotherapy subgroup (defined as the subgroup of patients not on tafamidis at study baseline). Changes included in this amendment concern the method of data analyses and do not impact study execution or the patient experience.

Establishing the efficacy of vutrisiran in the overall population is important because it is representative of current treatment practice, wherein many patients with ATTR amyloidosis (hereditary and wt) with cardiomyopathy are prescribed tafamidis as it is the only currently approved treatment available.

The rationale for analyzing the primary endpoint in the vutrisiran monotherapy subgroup is to enable demonstration of the potential clinical benefit of vutrisiran without any confounding effect of benefit from tafamidis. Patients already prescribed tafamidis for the approved cardiomyopathy indication were permitted to enroll in HELIOS-B, and there was no eligibility requirement that these patients needed to have manifested disease progression on tafamidis. Thus, patients on tafamidis at baseline, comprising approximately 40% of the enrollment into

HELIOS-B, are likely to have been receiving some degree of CV benefit from this medication throughout the trial. For this reason, the results from a pre-specified analysis in the vutrisiran monotherapy subgroup would provide the clearest demonstration of the potential clinical benefit of vutrisiran, without any confounding effect of benefit from concomitant tafamidis.

This amendment also restructures the existing secondary and exploratory endpoints such that specific endpoints were moved from exploratory to secondary and from secondary to exploratory based on the rationale below.

Changes included with Amendment 5 are outlined below:

Section(s)	Description of Change	Brief Rationale

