5.7.1.3. Component Analysis

The primary endpoint includes 2 components: all-cause mortality and recurrent CV events. The following will be summarized: the number of all-cause mortality (including death, heart transplant, and LVAD), the number of CV events (including CV hospitalization, indeterminate hospitalization, and urgent HF visit), the number and percentage of patients with at least one event. Vital status data after study discontinuation is not included in the above mortality component descriptive summary.

Inferential analyses for the component of all-cause mortality will include the vital status data collected after study discontinuation. The same statistical methods as that for the secondary endpoint of all-cause mortality (Section 5.7.2.2) will be used.

Inferential analyses for the component of recurrent CV events will be based on Poisson regression model with covariates including treatment, ATTR disease type, NYHA Class, age group, and baseline NT-proBNP as covariates, adjusting for the event follow-up time (i.e., including this duration as an offset). The overall population analysis will also include baseline tafamidis use and treatment-by-baseline tafamidis use interaction as covariates.

Recurrent CV events will be also analyzed using a joint frailty model (JFM) [Rondeau 2007] as a sensitivity analysis. For the JFM, the same covariates will be included for both the sub-model for recurrent CV events and the sub-model for all-cause mortality: treatment, ATTR disease type, NYHA Class, age group and baseline NT-proBNP group. The overall population analysis will also include baseline tafamidis use as a covariate. The baseline hazard functions for both recurrent CV events and all-cause mortality are approximated by piecewise constant functions. Details of the JFM methodology and implementation are provided in Appendix 9.6 .

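### SAP 9.6 reads a non-significant test of γ = 0 as little correlation between CV events and death, although the test can easily miss weak to moderate correlation; the consequence is limited to a sensitivity analysis

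*SAP*

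**What the plan says.** SAP Section 5.7.1.3 bases inference on the recurrent CV event component on Poisson regression and adds a second analysis: "Recurrent CV events will be also analyzed using a joint frailty model (JFM) [Rondeau 2007] as a sensitivity analysis".

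SAP Section 9.6 describes that model. Each patient has a frailty v, "which has a gamma distribution with unit mean and variance" θ. The CV event rate is proportional to v and the death hazard to v^γ, so γ measures how strongly death and CV events are linked.

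The section states that when γ = 0 the JFM and the model for recurrent events alone (the reduced model) give very similar estimates and variances. When γ > 0, the reduced model is described as "biased towards null or underestimated effects on recurrence rate", and the JFM as practically unbiased.

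Under the model-fit criteria it then says: "Model fit for JFM will be checked via the testing of" γ = 0, and "An insignificant result indicates little correlation between recurrent events and death which supports a reduced model". No significance level, type of test, margin for what counts as little, or interval for γ is stated, and the section shows no sign of blacked-out text at this point.

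**The concern.** The rule draws a conclusion of near-absence from a failure to reject. That would need either a demonstrated high chance of detecting any γ that matters, or a confidence interval that excludes such values. The SAP offers neither.

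On the SAP's own account the rule also has nothing to gain. If γ really is zero, the two models agree and preferring the simpler one adds little. If γ is positive and the test misses it, the rule lends support to the model that the SAP calls biased.

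The model-fit label is also inaccurate. Testing γ = 0 asks whether the frailty carries over to death. It does not examine the gamma shape of the frailty, the proportional effects or the piecewise-constant hazards. When θ is small, v is close to 1 and so is v^γ for any γ, so a non-significant result is then expected whatever γ is.

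At stake is what may be concluded. The Poisson analysis of this component does not model death jointly; the JFM does. A prespecified sentence would allow a non-significant γ to be cited as showing that death does not distort the component result. SAP Section 5.7 repeats efficacy analyses in the overall, monotherapy and background tafamidis populations, so the same underlying dependence could be called present in one and small in another through sample size alone.

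**Working it through.** **Inputs from the documents.** Protocol Section 3.4: "The planned enrollment for this study is 600 patients". The Amendment 5 summary describes patients on tafamidis at baseline as "comprising approximately 40% of the enrollment into" the trial. Hence monotherapy 600 × 0.60 = 360 and background tafamidis 600 × 0.40 = 240. Allocation is 1:1 and double-blind exposure lasts 33 to 36 months.

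**Inputs not in the documents (assumed).** The sample-size text is blacked out and the SAP gives no θ or γ. Assumed: θ = 0.5, 1 or 2; γ from 0 to 1; placebo 36-month mortality 15%, 25% or 35%; placebo CV event rate 0.4 per year; rate ratio 0.75; death hazard ratio 0.75; dropout 3% per year; two-sided 0.05. There is no plan figure to reproduce.

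**Method.** The Section 9.6 model was simulated and fitted by maximum likelihood with numerical integration over the frailty, using constant baseline hazards and treatment as the only covariate. There were 300 trials per scenario (Monte Carlo standard error at most 0.03). With γ = 0 the test rejected in 3% to 8% of trials, so its size is about right.

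**Share of trials in which the Wald test misses a real γ** (1 − power; the range runs from 35% down to 15% placebo deaths):

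| θ | γ | N = 600 | N = 360 |
|---|---|---|---|
| 0.5 | 0.5 | 58–89% | 81–90% |
| 0.5 | 1.0 | 11–50% | 32–78% |
| 1 | 0.25 | 62–84% | 79–90% |
| 1 | 0.5 | 12–53% | 32–71% |
| 1 | 1.0 | 0–5% | 1–26% |
| 2 | 0.25 | 12–50% | 37–79% |
| 2 | 0.5 | 0–5% | 2–25% |
| 2 | 1.0 | 0–1% | 0–1% |

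The likelihood-ratio test usually does better. For θ = 1 and γ = 0.5 it misses 7–40% at N = 600 and 20–54% at N = 360.

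**Hand check.** At N = 600, θ = 1, γ = 0.5 and 15% deaths, the standard error of γ is about 0.26. Approximate power is Φ(0.5/0.26 − 1.96) = Φ(−0.04) = 0.48, against 0.47 simulated. With that standard error, even an estimate of exactly zero has a 95% interval of ±1.96 × 0.26 = ±0.51, which does not exclude γ = 0.5.

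**What γ = 0.5 means.** For a gamma frailty, Var(log v) is the trigamma function at 1/θ: 0.645 for θ = 0.5 and 1.645 for θ = 1. A one-SD rise in log frailty multiplies the death hazard by exp(0.5 × √0.645) = 1.49 or exp(0.5 × √1.645) = 1.90.

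**Smaller subgroup.** A second set of simulations used rate ratio 0.70, death hazard ratio 0.65, about 15% deaths overall, the likelihood-ratio test and 150 trials per cell. For γ = 0.5 it gave misses of 33%, 53% and 65% at N = 600, 360 and 240 with θ = 1, and 69%, 79% and 83% with θ = 0.5.

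**Effect on the treatment estimate.** Among trials where the likelihood-ratio test missed, the reduced-model rate ratio was at most about 0.007 closer to 1 than the JFM (0.781 against 0.774 at N = 360, 35% deaths, θ = 0.5, γ = 1). The second set gave gaps of 0.003 to 0.015. The crude Poisson ratio was at most about 0.02 closer to 1 where likelihood-ratio power was below 80%. Larger gaps arise under strong dependence (0.796 against 0.770 at N = 360, 35% deaths, θ = 2, γ = 1), but there the test detected γ in every simulated trial.

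**The case against.** The best reply is that the test decides nothing. SAP Section 5.7.1.3 plans both the Poisson and the JFM analysis without any condition on γ. A reader might infer from Section 9.6 that a non-significant result replaces the JFM with the reduced model, perhaps differently by population. No text says so: nothing cancels the JFM or changes a reported analysis. Recurrent CV events alone are not among the five families in SAP Section 4.6, so no alpha-controlled conclusion depends on γ. Death is also handled elsewhere: in the primary composite, in the all-cause mortality analyses and as the first step of the win ratio. All of this stands.

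A reader might also infer that a trial of this size generally cannot detect the correlation. That is not supported. The inputs that decide it are all assumed, and strong dependence is found in most trials at either size. The misses concentrate where dependence is weaker and the reduced model is closest to adequate. This too stands.

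Finally, Section 9.6 already has γ and θ estimated, so much of the remedy is in place. That is true of estimation, but the SAP does not commit to intervals, and the interpretive sentence remains. None of these points makes non-significance a valid basis for concluding little correlation.

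**Conclusion.** The sentence is wrong as written: it is an interpretation rule, within a sensitivity analysis, that the data may be unable to support. For weak to moderate dependence the chance of a miss is substantial, though the figures are ranges over assumptions. The simulations omit covariates; adjusting for disease type, NYHA class, age and NT-proBNP, as the SAP plans, would tend to lower residual θ and so the power.

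The harm is an unsupported conclusion, possibly differing between populations because of their size. It is not a materially wrong estimate, and the bias does not flatter the drug. The change is worth making because the rule has no benefit and removing it is nearly free. It has no bearing on the validity of the primary analysis.

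**What to change.** In SAP Section 9.6, delete the sentence that takes a non-significant result as support for the reduced model, and stop describing the test of γ as a check of model fit. Put in its place, in substance:

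> The JFM and Poisson estimates for recurrent CV events are reported side by side in each analysis population, whatever the p-value for γ. Estimates of γ and θ are given with 95% confidence intervals. A non-significant γ is not read as absence of correlation and is not used to prefer a model that leaves out death.

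The cost is SAP wording only: both analyses are already planned and the fit already estimates γ and θ. The downside is that a wide interval for γ will be on display, mainly in the monotherapy and background tafamidis subgroups. That width is the information a reader needs.

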9.7. Imputation for Partial or Missing Dates

Inpatient admission or urgent/unscheduled healthcare visits:

For partial/missing dates, the imputation will be done for discharge (end) dates first, followed by admission (start) dates.

If the location of the visit is not ‘inpatient admission’:

End date imputation:

- If only day is missing: if the start date is complete, impute the end date as the start date, otherwise impute as the last day of the month.
- If both month and day are missing:
 - if the start date is complete, impute the end date as the start date.
 - if the start date has missing day only, impute the end date as the last day of the same month as the start date.
 - if the start date has both month and day missing, impute the end date as June 30. If this results in a date before the first dose date, set the end date to the last day of the month and year of the first dose date.
- If the date is completely missing:
 - if the start date is complete, impute the end date as start date.
 - if the start date has missing day only, impute as the last day of the same month of the start date.
 - if the start date has missing month and day, the month and day are imputed as June 30, and year is the same as the start date. If this results in a date before the first dose date, set the end date to the last day of the month and year of the first dose date.

Start date imputation:

- if only day is missing and the year and month are the same as the end date, impute the missing day the same as the end date.
- if both day and month are missing, impute the missing day and month the same as the end date.
- if complete missing, impute the missing date the same as the end date.

If the location of the visit is ‘inpatient admission’:

End date imputation:

- If only day is missing: if the start date is complete, impute the end date as the day after the start date, otherwise, impute as the last day of the month.
- If both month and day are missing:
 - if the start date is complete, impute the end date as the day after the start date.
 - if the start date has missing day only, then impute the end date as the last day of the same month as start date.
 - if the start date has missing month and day, impute the end date as June 30, if this results in a date before the first dose date, then set to the last day of the month and year of the first dose date.
- If the date is complete missing:
 - if the start date is complete, impute the end date as the day after the start date.
 - if the start date has missing day only, impute as the last day of the same month of the start date.
 - if the start date has missing month and day, impute as the last day of the month and year as the first dose date.

Start date imputation:

- if only day is missing
 - if the start date and end date have the same month, impute the missing day as the day before the end date.
 - if the start date and end date have different months, impute as the last day of the month.
- if both day and month are missing, impute as the date before the end date.
- if complete missing, impute the missing date as the date before the end date.

Medications:

- For medications with missing month/day for start or end dates:
 - For start dates, missing month will be imputed as January and missing day will be imputed as the first day of the month.

- For end dates, missing month will be imputed as December and missing day will be imputed as the last day of the month.
- For medications with completely missing start or end dates:
 - Missing start date will be imputed as one day prior to the first dose of study drug. If the imputed start date is after the collected end date, the end date will be used as the imputed start date.
 - Missing end date will be imputed as the earliest date of study discontinuation date, cutoff date, or death date.

Adverse events and Procedures:

Partial or missing AE or procedure end dates will not be imputed. For AE or procedure start date:

- If year is missing, set to the first dose date. If this leads to a date after the end date (when end date is available with partial or complete information), set to the end date.
- If year is not missing, but both day and month are missing:
 - If year of the start date is equal to the year of the first dose date, set to the first dose date.
 - If year of the start date is not equal to the year of the first dose date, impute the missing day and month of the start date as January 1st.
 - If the imputed date leads to a date after the end date, impute the missing day and month of the start date using the day and month of the end date.
- If only day of the start date is missing:
 - If the year of the start date is equal to the year of the first dose date, and the month of the start date is equal to the month of the first dose date, impute the missing day of start date using the day of the first dose date.
 - Otherwise, impute the missing day of the start date as 1.
 - If the above leads to a date after the end date, impute the missing day of the start date using the day of the end date.

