5.7.1.2. Primary Analysis

The primary endpoint of all-cause mortality and recurrent CV events CCI [REDACTED]

CCI

The primary analysis will include events occurring during the DB period. For each patient, the Event Follow-up time will be calculated as the time from the first dose of study drug to the last Event Follow-up date (Table 3). Deaths collected after study discontinuation are not included in the analysis.

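### SAP 9.7 sets no upper limit on imputed dates of hospitalizations and urgent HF visits, so an event that preceded death or study discontinuation can be dated after it and go uncounted

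*SAP*

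**What the plan says.** SAP 9.7 gives a separate rule for inpatient admissions and urgent or unscheduled visits. It fixes the order: "the imputation will be done for discharge (end) dates first, followed by admission (start) dates".

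- **Day missing on both dates.** The end date rule is "otherwise impute as the last day of the month", for admissions and other visits alike.
- **Month and day missing on both dates.** The rule is "if the start date has both month and day missing, impute the end date as June 30". Its only safeguard is a lower one: "If this results in a date before the first dose date, set the end date to the last day of the month". The month meant there is the one in which dosing began. (One inpatient branch, with a completely missing discharge date and a year-only admission date, uses the month of first dose instead.)
- **Start date.** For a visit that is not an admission, when the months agree: "impute the missing day the same as the end date". For an admission: "if the start date and end date have the same month, impute the missing day as the day before the end date".

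SAP 5.7.1.2 states: "The primary analysis will include events occurring during the DB period". Table 3 ends event follow-up at the first OLE dose for patients who enter the OLE. For the others it ends at the earliest of last known alive/death date, study discontinuation and first dose plus 1120 days. SAP 4.2 compares start dates with the data cutoff.

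For medications, the same section 9.7 sets a completely missing end date to the earliest of study discontinuation, cutoff and death. The visit rule has no such limit.

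**The concern.** Month end and 30 June are arbitrary points inside the known month or year, and follow-up may have ended before them. A visit cannot follow death. SAP Table 6 also says that patients who leave the study stop reporting CV events. For such a patient, a visit known only by the month of death or discontinuation belongs before that date, but the rule puts it after unless follow-up happened to end at month end.

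Read literally, the event then lies outside Table 3 follow-up, and no visible text says what to do with it. The same dates feed the win ratio's event counts over common follow-up (SAP 9.2). They also feed the multiple imputation of SAP 9.3, which fills in events from study discontinuation onward. Without a stated rule, someone must decide at programming time whether to drop, move or keep the record.

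**Working it through.** **Inputs.** The dating rules are those of SAP 9.7 and the end of follow-up is that of Table 3. I take the start date as the event date; SAP 4.2 uses it for the cutoff, but no visible text states it for the endpoint. Table 3's own arithmetic is sound: 156 × 7 + 28 = 1120 days, and 1120 + 183 = 1303 days.

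**Worked example.** The true event is on 5 March 2023 and the patient dies on 20 March 2023.

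| Known for both dates | Imputed start, admission | Imputed start, other visit |
|---|---|---|
| Month and year | 30 March | 31 March |
| Year only (end-date year recorded) | 29 June | 30 June |

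All four dates fall after death.

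**When the rule bites.** Both dates must be incomplete. A complete start date is never moved, and a complete end date limits the imputed start. An admission that ends in death on a known date is therefore safe.

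**Month-only events, full follow-up.** Assume a constant event rate over 36 months. The calendar month in which follow-up ends contains half a month of exposure on average, so the share lost is 0.5/36 = 1.4%. Counting a whole month would give 1/36 = 2.8%, twice what these assumptions support.

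**Year-only events, full follow-up.** Assume follow-up ends uniformly through the year. It ends before 30 June with probability 0.5, and mean exposure in that final year is then 0.25 years. Over 3 years the share lost is 0.5 × 0.25/3 = 4.2%.

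**Many early stops.** A simulation applied the rules literally. Its assumptions are not from the documents:

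- first dose uniform over about 20 months;
- half of patients ending follow-up at 60–1007 days and half at 1008–1092 days;
- one event per patient, uniform over follow-up.

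Results for events with both dates partial:

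- **Month-only:** 2.5% (admissions) to 2.8% (other visits) lost. Of events in the final calendar month, 88% to 94% are lost.
- **Year-only:** about 8% lost.
- **Opposite direction:** about 23% of year-only events in the 180 days after follow-up are pulled back into the DB period.

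One event per patient gives short follow-up extra weight. With a constant rate, mean follow-up is (533.5 + 1050)/2 = 792 days. Month-only loss is then about (30.4375/2)/792 = 1.9%. Year-only loss is 0.125 × 365.25/792 = 5.8%. Both lie inside the ranges above.

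**Cutoff.** The Amendment 3 summary in the protocol says enrollment was completed in August 2021. Counting 144 weeks (1008 days) from 31 August 2021 gives 4 June 2024. SAP 4.2 places the cutoff at about the last OLE entry. If the cutoff fell in early June 2024, every year-only 2024 visit dated 29 or 30 June would lie after it. The actual cutoff date is not given.

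**The case against.** **The primary analysis may not use these dates.** It counts CEC-adjudicated events; investigator-assessed events form a separate analysis (SAP 5.7.1.4.2). The 9.7 rule is worded like the investigator's eCRF form described in SAP 4.8. The CEC charter is not available, and parts of 4.8 and 5.7.1.2 are redacted. A reader might infer that double-blind events are certainly lost from the primary analysis, but the visible text does not establish that. What remains is that 9.7 is the only visible dating rule for these visits, and it covers the investigator-assessed analysis in any case.

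**Events near OLE entry.** A reader might also infer that a partial date falling after the first OLE dose hides a double-blind event, and that the date should be moved to the day before that dose. This does not follow. Patients continue to report events in the OLE, so the true date may lie on either side. If OLE entry and event are both uniform within the month, about half of such events are truly open-label.

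**Study discontinuation is less certain than death.** Protocol 6.1 and 8.1.1 allow hospitalizations to be obtained from medical records after a patient leaves early. That such an event must have come before discontinuation rests on the statement in SAP Table 6.

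**Few events, no favoured arm.** The rule needs two incomplete dates on one record, and data are cleaned before lock. Table 3 also moves the discontinuation date to the death date when death follows within 30 days, which removes some cases. The rule is the same in both arms, and the 30 June convention also errs in the other direction. Nothing in the documents supports a claim of bias toward either arm.

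**Conclusion.** The gap is real and minor. As written, the rule can give a hospitalization or urgent visit a date after the patient's death or study discontinuation, and such an event then falls outside the counted follow-up. This holds for the investigator-assessed analysis. It holds for the primary analysis unless the charter or redacted text dates adjudicated events differently.

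Among events with both dates incomplete, the loss is about 1.4% of month-only events with full follow-up, rising to about 2.8% if many patients stop early. For year-only events it is roughly 4% to 8%. These shares rest on assumed follow-up patterns and on events spread evenly over follow-up; clustering of events near death would raise them. They apply only to partially dated events, whose number is not given, so the effect on the hazard ratio is probably small. The reason to act is that the rule can produce an impossible date in endpoint data and leaves its handling open, although the same section already limits medication end dates.

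**What to change.** Add to the visit rule in SAP 9.7: if an imputed start or end date is later than the earliest of death, heart transplant or LVAD placement, study discontinuation (after the 30-day adjustment in Table 3) and analysis cutoff, and the known month or year is compatible with an earlier date, set it to that earliest date. Applying the cap to the end date first lets the existing start-date rule follow from it.

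Do not cap automatically at the day before the first OLE dose. Where the visit form or collection period does not show on which side of that dose the event fell, prespecify a treatment-blind convention.

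Also state whether adjudicated events take the 9.7 date or a date set by the CEC; a cross-reference to the charter is enough. Report the number of partial dates by arm.

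The cost is a few sentences in the SAP and a line or two of code, with no new data collection.
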